6.1 PRIMARY ENDPOINTS	12
6.2 SECONDARY ENDPOINTS	13
7 SAFETY MANAGEMENT	13
7.1 CLINICAL ADVERSE EVENTS	13
7.2 ADVERSE EVENT REPORTING	13

8	STUDY ADMINISTRATION.....	13
8.1	TREATMENT ASSIGNMENT METHODS.....	13
8.1.1	Randomization.....	13
8.2	DATA COLLECTION AND MANAGEMENT	14
8.3	CONFIDENTIALITY.....	15
8.4	REGULATORY AND ETHICAL CONSIDERATIONS.....	15
8.4.1	Risk Assessment.....	15
8.4.2	Potential Benefits of Trial Participation	16
8.4.3	Risk-Benefit Assessment	16
8.5	RECRUITMENT STRATEGY	16
8.6	INFORMED CONSENT/ASSENT AND HIPAA AUTHORIZATION (AYA/CAREGIVERS).....	16
8.6.1	Consent with Waiver of Documentation.....	17
8.7	INFORMED CONSENT (ONCOLOGY HEALTH CARE PROVIDERS).....	17
8.7.1	Consent with Waiver of Documentation.....	17
8.8	PAYMENT TO SUBJECTS.....	18
8.8.1	Families (AYA and Caregivers)	18
8.8.2	Oncology Health Care Providers.....	18
9	PUBLICATION.....	18
10	REFERENCES	18

ABBREVIATIONS AND DEFINITIONS OF TERMS

AE	Adverse Event
AYA	Adolescents and Young Adults with Cancer
BAA	Business Associates Agreement
CFR	IRB Code of Federal Regulations
CI	Confidence Interval
DECIDES	D eciding about E nrolling on a C linal I ntervention trial: D ecision aid for E ducation and S upport
DECIDES+ coach	DECIDES intervention with coach-assisted support
EPIC	Electronic Health Record
NCI	National Cancer Institute
PHI	Protected Health Information
SAE	Significant Adverse Event
T1	Time Point 1: Baseline Assessment
T2	Time Point 2: Post-Intervention Assessment
T3	Time Point 3: Semi-Structured Qualitative Interview

ABSTRACT

Context:

Adolescents and young adults with cancer (AYA) have limited involvement in treatment decision-making, do not fully understand cancer treatments (including clinical trials), and are vulnerable to acute distress undermining their decision processes at diagnosis. Research on how to increase involvement of AYA in treatment decision-making may be critical for addressing observed disparities in AYA enrollment in clinical trials and cancer outcomes, but few empirical studies have examined decision process or addressed AYA engagement in the cancer treatment decision.

Objectives:

Specific aims of the proposed study are to establish DECIDES acceptability, usability, and feasibility, evaluate preliminary efficacy for improved decision-making processes, and identify implementation strategies for future dissemination.

Study Design:

This study will use mixed methods in a hybrid design to evaluate a web-based decision support intervention (DECIDES = AYA Deciding about Enrolling on a Clinical Intervention Trial: Decision Aid for Education and Support) to increase involvement and improve decision-making processes for AYA, their caregiver(s), and oncology health care providers.

[figure not shown]
Setting/Participants:

We expect to enroll up to 65 family units in order to produce 50 evaluable family units, consisting of AYA (ages 15-24 years that are within six weeks of receipt of a new or relapsed leukemia/lymphoma, solid tumor, or brain tumor diagnosis at the Children's Hospital of Philadelphia) and their caregiver(s) (primary and secondary, if applicable) that are randomized to participate in Usual care (n=10 family units), DECIDES (n=20 family units), or DECIDES + coach (n=20 family units). AYA that are 18 and older may participate alone, without a caregiver. Approximately 25 oncology health care providers that participate in decision-making about cancer treatment with enrolled AYA and caregiver(s) will be invited to participate in this study.

Study Interventions and Measures:

DECIDES is a developmentally appropriate engaging and interactive web-based decision aid that has been designed to addresses health literacy and includes components to increase knowledge of cancer and cancer treatments (including clinical trials), address attitudes to cancer treatments (including clinical trials) and weigh perceived barriers and benefits of standard treatment or a cancer clinical trial relative to values. We will evaluate indicators of acceptability and feasibility, as well as barriers and facilitators to implementation, and compare decision-making involvement, shared decision-making, and decision processes for AYA, caregiver(s), and oncology health care providers.

FIGURE 1: STUDY DIAGRAM

1 BACKGROUND INFORMATION AND RATIONALE

Approximately 21,400 adolescents and young adults (AYA) ages 15 to 29 years were diagnosed with cancer in 2000, which is nearly 3 times that of patients diagnosed in the first 15 years of life.⁽⁷⁾ Contrary to younger age groups, 5-year survival and mortality reduction rates for AYA with cancer have remained stagnant.^(7,9,19) Reasons for this disparity are multi-factorial and include reduced participation in therapeutic clinical trials, which may reduce direct medical benefits and hinder treatment advances.⁽¹⁰⁻¹²⁾ The National Cancer Institute has advanced initiatives to increase AYA's access to cancer clinical trials, but emerging evidence indicates that AYA do not experience shared decision-making⁽²⁰⁾ and are less likely to enroll when offered a clinical trial.^(13,21)

AYA Development and Medical Decision-Making. The American Academy of Pediatrics provides that children be involved in medical decision-making to the extent that they are capable.⁽⁷⁸⁾ Children as young as age nine may have the cognitive capacity to assent (i.e., engage in the decision-making process for clinical trials about participation);^(79,80) however, factors other than age contribute to competence in medical decision-making.⁽⁸¹⁾ Optimal AYA decision-making includes the ability to set adaptive goals, work on more than one goal at a time, and overcome obstacles that might arise while evaluating options.⁽⁸²⁾ AYA decision-making abilities may be similar to that of adults when they are properly educated about the diagnosis and provided information about treatment options;^(86,83) although, the way in which participation is framed must be appropriate to cognitive capacity and level of maturity.^(84,85) In these circumstances, even younger AYA can manifest fundamental abilities needed for informed decision-making about medical treatments, such as the ability to weigh future consequences of their decisions, and the cognitive maturity to make such decisions based on their experience with cancer, personal values as emerging adults, and their acceptance of the possibility of death.⁽⁸⁶⁾

AYA involvement in clinical trial decisions is important but limited. Our research found that AYA involvement in clinical trial decision-making at diagnosis was more limited than preferred;⁽¹⁾ a recent review of the literature echoes this finding.⁽²²⁾ Highlighting the critical importance of improving decision-making processes in addressing AYA clinical trial enrollment, and consistent with other studies,^(23,24) AYA described presentation of information as ineffective in promoting understanding of treatment options, and caregivers and providers were challenged to maintain AYA engagement in treatment planning. Involvement in medical decision-making may have positive effects on AYA adaptation,⁽²⁵⁻²⁷⁾ but understanding of complex AYA clinical trial decision-making processes is only emerging.⁽²⁵⁻²⁹⁾ While most AYA have capacity,⁽³⁰⁾ shared decision-making with caregivers and providers varies.^(25-29, 31) Snethen and colleagues⁽³¹⁾ described developmental patterns of parent-child research decision-making,⁽³¹⁾ and Whitney and colleagues⁽³²⁾ outlined a decisional priority model in which characteristics of cancer clinical trial decisions interact with potential for cure to inform AYA involvement.

Unique aspects of AYA decision-making about cancer clinical trials. Newly diagnosed AYA and their caregivers are given extensive, complicated information on diagnosis, treatment, and clinical trials in context of intense emotions at diagnosis and short time allotted for decision-making.^(33,34) Relapse initiates new worries and distress. Thus, deficiencies in understanding are prevalent among parents who enroll their child on a cancer

clinical trial,^(35,36) and adolescents and parents need support to distinguish clinical trials from standard treatment.^(33,37-39) Youth with cancer and their parents are motivated to participate in research;⁽⁴⁰⁻⁴²⁾ yet, AYA note enrollment barriers of fear of toxicity, preference for standard treatment, and lack of family support.^(43,44)

Decision interventions may support AYA involvement in cancer treatment decisions.

AYA and their primary caregivers may benefit from the promise of decision support tools that increase understanding of cancer and cancer treatments, and clarify values vis-à-vis clinical trial enrollment.^(25,45) Decision interventions, primarily designed to support shared (patient, caregiver, and health care provider) decision-making for decisions of equipoise, provide a framework for decision-making regarding cancer clinical trial enrollment.^(45,46) Further, increased decision satisfaction and self-efficacy and decreased decision conflict and regret result from decisions that align with values.^(6,47,48)

Development and evaluation of interventions to improve decision-making for AYA and their families is critical.⁽⁴⁹⁻⁵¹⁾ The proposed study is highly innovative, as it is the first in the United States to use “best practice” mixed methods to test a rigorously developed decision support intervention for AYA and their primary caregivers⁽⁵²⁾ in the context of real time (versus hypothetical or retrospective) cancer treatment decision-making.^(53,54) Findings from a recent Australian-based pilot study assessing a parent and adolescent cancer clinical trial decision aid (retrospective to the actual decision) indicate benefit and relevance, but further evaluation is needed to assess the impact on families making an active treatment decision including whether to enroll in a clinical trial.⁽⁵⁵⁾

1.1 Relevant Literature and Data

Data from our series of mixed method studies examining pediatric clinical trial decision-making informed DECIDES development and the proposed measurement strategy, study design, and value clarification exercise.^(1,56-58)

1.1.1 Pediatric Research Participation Questionnaire (PRPQ-AYA)

This study capitalizes on our federally-funded measure, the Pediatric Research Participation Questionnaire, modified to assess attitudes to cancer clinical trials for AYA and their caregivers.^(1,56-58) Results support a 4-factor structure, and reliability and validity, for caregivers (direct benefit, mistrust, trust in the health care team and safety of research, and opportunity cost) and AYA (mistrust/no perceived benefit, safety of research/perceived benefit, direct benefits/practical considerations; altruism, access to treatments, and practical issues, and social support for research participation). Perceived barriers and benefits are particularly relevant to AYA clinical trial decision-making and inform the DECIDES value clarification exercise.

1.1.2 AYA Cancer Clinical Trial Decision-Making

We evaluated AYA with cancer, primary caregiver, and oncology provider Phase III clinical trial decision-making experiences.⁽¹⁾ From content analysis, AYA perceived that they had no role (38.4%) or a minor role (30.8%) in the clinical trial enrollment decision; they conveyed a sense of resignation because they viewed themselves as relying on their parents to make treatment decisions at diagnosis. Caregivers and providers felt challenged to include AYA in the treatment decision-making process at diagnosis, and providers noted uncertainty in how

to provide balanced information about treatment options and minimize coercion. AYA and caregivers who refused a Phase III clinical trial cited prolonged treatment with limited benefit, but many AYA and caregivers did not accurately remember whether the cancer treatment had been standard of care or on a clinical trial.

1.1.3 DECIDES Development

In collaboration with our stakeholders, and using The NCI Health Communication Model,⁽⁵⁹⁾ we followed the Informed Medical Decisions Foundation procedures⁽⁴⁻⁶⁾ to develop DECIDES. First, we outlined content in storyboard format based on: 1) Health Belief Model and Theory of Reasoned Behavior;^(2,3) 2) review of the literature on AYA with cancer; 3) results of our studies of AYA decision-making and the PRPQ measure of perceived benefits and barriers to clinical trial enrollment;^(1,56-58) (4) stakeholder input from our hospital's AYA Patient Steering Committee, their primary caregivers, and a Scientific Advisory Committee; (5) recent AYA decision support for AYA recommendations;⁽¹⁸⁾ and (6) decision aid development guidelines and decision support research in adult oncology.⁽⁴⁻⁶⁾ DECIDES is web-based with multi-model, graphically interesting content written for low health literacy. Content includes information to increase knowledge of cancer, treatment, and clinical trials, fact or fiction to address attitudes about cancer treatment and clinical trials, a value clarification exercise to consider goals for life vis-à-vis goals for treatment, and resources to increase knowledge and improve decision processes. Results of the value clarification exercise, and perceived treatment barriers and benefits, are emailed to the provider. The last step in DECIDES development entailed revision of the website components in an iterative process based on feedback from scientific experts and stakeholders.

1.2 Compliance Statement

This study will be conducted in full accordance all applicable Children's Hospital of Philadelphia Research Policies and Procedures and all applicable Federal and state laws and regulations including 45 CFR 46. All episodes of noncompliance will be documented.

The investigators will perform the study in accordance with this protocol, will obtain consent and assent, and will report unanticipated problems involving risks to subjects or others in accordance with The Children's Hospital of Philadelphia IRB Policies and Procedures and all federal requirements. Collection, recording, and reporting of data will be accurate and will ensure the privacy, health, and welfare of research subjects during and after the study.

2 STUDY OBJECTIVES

2.1 Primary Objective (or Aim)

The primary objective of this study is to assess the acceptability and feasibility of DECIDES using mixed methods and use results to inform implementation strategies for future dissemination.

Hyp 1a. Based on AYA, caregiver(s), and oncology health care provider ratings, and usage analytics, DECIDES will be acceptable and feasible during treatment decision-making within 6 weeks of diagnosis.

Hyp 1b. Qualitative interviews with AYA and caregiver(s) (randomized to DECIDES and DECIDES + coach) and oncology health care providers will confirm acceptability and feasibility ratings and provide specific information regarding timing, utility, barriers/facilitators, ease of use, and modifications to DECIDES for future implementation.

Hyp 1c (exploratory). DECIDES + coach will be rated more usable than DECIDES alone.

2.2 Secondary Objectives (or Aim)

The secondary objective is to evaluate preliminary efficacy of DECIDES using a randomized trial.

Hyp 2a. AYA randomized to DECIDES and DECIDES + coach will report greater involvement in and shared decision-making than AYA assigned to Usual Care.

Hyp 2b. AYA and caregiver(s) randomized to DECIDES and DECIDES + coach will report more positive decision-making processes (greater knowledge of their cancer and clinical trials, more balanced attitudes toward clinical trials, and more decision certainty, satisfaction and self-efficacy) compared with those assigned to Usual Care.

Hyp 2c. For DECIDES and DECIDES + coach participants who are offered enrollment on a clinical trial, the enrollment decision (yes/no) will align with AYA values.

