5 STUDY EVALUATIONS AND MEASUREMENTS

5.1 Electronic Health Record Review

Medical information will be abstracted from the AYA patients' electronic health record (EPIC) for the following purposes:

- Enrollment Decision
- Demographics
- Diagnosis, date of diagnosis, age at diagnosis
- Intensity and types of treatments received (Using the Intensity of Treatment Rating-III)

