5.3 Semi-Structured Qualitative Interview

A semi-structured, qualitative interview guide designed by the study team for use with AYA and caregiver(s) (assigned to DECIDES or DECIDES + coach), and oncology health care providers. The purpose of the interview is to obtain further information from participants about the process of treatment decision-making and their experience using DECIDES, the decision aid. Participants will be interviewed by a study team member via remote video conference software (Microsoft Teams). All interviews will be audio and/or video recorded and professionally transcribed (by a CHOP-approved vendor with a BAA in place), and the interview data will be analyzed.

Table 1. Measures

Construct	Measure	Administration	
		T1	T2
Demographics	Electronic Health Record; AYA/Caregiver Self-Report	AYA, CG	
Treatment Intensity	Intensity of Treatment Rating Scale (ITR-3) ⁽⁹⁹⁾	PR	
Acceptability ^(D)	Acceptability of the Decision Aid ⁽⁶⁾		AYA, CG
Usability ^(D)	The Systems Usability Scale ^(36,71)		AYA, CG, PR
AYA Involvement in Shared Decision-Making	Control Preferences ^(74,75)		AYA, CG
	Physician Decision-Making Scale ⁽¹⁰⁰⁾		AYA, CG
	Shared-Decision Making Questionnaire (SDM-Q-9) ⁽⁹⁴⁾		AYA, CG
Knowledge	AYA Hope Survey: Information Need ^(76,77)	AYA, CG	
	Knowledge of Clinical Trials ⁽⁶⁴⁾	AYA, CG	AYA, CG
Attitudes to Clinical Trials	Pediatric Research Participation Questionnaire	AYA, CG	AYA, CG
Alignment of Decision with Values	(PRPQ) ^(15,16)		AYA, CG
Decision-Making	Certainty	Decisional Conflict Scale ⁽⁶⁵⁾	AYA, CG
	Satisfaction	Satisfaction with Decision Scale ⁽⁶⁶⁾	AYA, CG
	Self-Efficacy	Decision Self-Efficacy Scale ⁽⁶⁷⁾	AYA, CG
	Regret	Decision Regret Scale ⁽⁷²⁾	AYA, CG
Health-Related Quality of Life	PROMIS Parent Proxy Profile-25 ⁽⁹⁸⁾	CG	CG
	PROMIS Pediatric Profile-25 ⁽⁹⁷⁾	AYA (15-17)	AYA (15-17)
	PROMIS-29 Profile ⁽⁹⁶⁾	AYA(18-24)	AYA(18-24)
*Distress	Distress Thermometer ⁽⁷³⁾	AYA, CG	AYA, CG
*Valence and Arousal	Affective Slider ⁽⁸⁷⁾	AYA, CG	
*Awareness of Feeling Emotions	Affective Orientation (AO15) ⁽⁸⁸⁾	AYA, CG	
*Developmental Status	Developmental Task Questionnaire ^(89,92)	AYA	
*Psychosocial Maturity	Consideration of Future Consequences ⁽⁹⁰⁾	AYA, CG	
	Psychosocial Maturity Inventory ⁽⁹⁵⁾	AYA	
	Emotion Regulation Questionnaire ⁽⁹¹⁾	AYA, CG	
*Problem-Solving	Family Assessment Device (FAD): Problem-Solving ⁽⁹³⁾	AYA, CG	
Semi-Structured Qualitative Interview ^(D)	DECIDES Interview Guide		AYA, CG, PR

* = Covariate

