(D) = measure for participants randomized to DECIDES or DECIDES + coach only

T1 = Pre-Intervention; T2 = Post-Intervention; AYA = Adolescent/Young Adult; CG = Caregiver; PR = Health Care Provider

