6.2 Secondary Endpoints

The secondary objective is to evaluate preliminary efficacy of DECIDES using a randomized trial.

Hyp 2a and Hyp 2b. Because all measures are continuous, the primary analyses will be summarizing mean and 95% CI by groups and two-sample t test comparing groups for the post-intervention outcome measures. With the sample size of 20 family units for each DECIDES group and 10 family units for usual care, we will have 80% power to detect an effect size of 1.26 (that is, mean difference between the two groups is 1.26 x Standard Deviation).

Hyp 2c. Each AYA and caregiver will have two value scores: Σ factors endorsed as supporting enrollment/ Σ factors endorsed as not supporting enrollment. Consistency of value to enrollment decision will be evaluated with Tetrachoric correlation with 95% CI.

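### Hyp 2c is listed as preliminary efficacy but has no between-arm contrast, so value–decision alignment in the DECIDES arms alone cannot show an effect of DECIDES

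*Combined protocol and SAP*

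**What the plan says.** Section 2.2 gives one secondary objective: "The secondary objective is to evaluate preliminary efficacy of DECIDES using a randomized trial". Three hypotheses follow.

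- Hyp 2a is comparative: AYA in the DECIDES arms "will report greater involvement in and shared decision-making than AYA assigned to Usual Care". Hyp 2b is likewise set against Usual Care.
- Hyp 2c is not comparative: "For DECIDES and DECIDES + coach participants who are offered enrollment on a clinical trial, the enrollment decision (yes/no) will align with AYA values". Usual Care is not mentioned.

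Section 6.2 describes the Hyp 2c analysis in two sentences. The first, "Each AYA and caregiver will have two value scores", carries no arm restriction; it defines the scores by the factors endorsed for and against enrollment and names no instrument. The second gives the statistic: "Consistency of value to enrollment decision will be evaluated with Tetrachoric correlation with 95% CI". No null value, threshold or between-arm contrast is stated.

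On data sources, Table 1 (section 5.3) has a row "Alignment of Decision with Values" tied to the PRPQ and completed by AYA and caregivers at T2. That row lacks the (D) mark, which the footnote defines as "measure for participants randomized to DECIDES or DECIDES + coach only". Section 4.1.4 has all three arms, Usual Care included, complete T2. Section 5.1 lists "Enrollment Decision" among the items abstracted from the AYA patients' health records, without restriction by arm.

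**The concern.** An efficacy claim needs some account of what would have happened without the intervention. Families who lean towards a trial will tend to enroll, and those who lean against it will tend to decline, whether or not they have seen a decision aid. A positive correlation in the DECIDES arms is therefore expected even if DECIDES has no effect. Hyp 2c nevertheless appears under preliminary efficacy, beside two hypotheses that do use the randomized comparator.

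What is at stake is interpretation. A positive correlation reported under this objective could be read as a sign of efficacy and carried into the planning of a later trial, when it might describe only what usual care already achieves.

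**Working it through.** **1. No planned figure to reproduce.** The documents give no sample size, power or precision for Hyp 2c. The 1.26 SD at 80% power in section 6.2 belongs to the mean comparisons of Hyp 2a and 2b and says nothing about alignment.

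**2. The passages side by side.**

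| Element | Where | Usual Care included? |
|---|---|---|
| Hyp 2c population | 2.2 | Not named |
| Value scores | 6.2 | No arm restriction; source not named |
| Alignment measure (PRPQ, T2) | Table 1 | Yes, no (D) mark |
| T2 assessment | 4.1.4 | Yes, all three arms |
| Enrollment decision | 5.1 | No arm restriction |
| Whether a trial was offered | Not a listed variable | – |
| Value clarification exercise | 4.1.3 | Described only in the DECIDES arms |

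The restriction to the DECIDES arms is thus in 2.2 and is not repeated in 6.2. On either text, no between-arm contrast is specified.

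**3. How much alignment could occur with no effect of DECIDES.** The documents give no alignment rate, so the inputs are assumed: 70% of families have net-positive values, 70% enroll, and the two are linked by a bivariate normal with correlation ρ. If p is the probability of being positive on both, agreement = p + (1 − 0.7 − 0.7 + p) = 2p − 0.4.

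- ρ = 0: p = 0.490, agreement 58%
- ρ = 0.4: p = 0.542, agreement 68%
- ρ = 0.6: p = 0.573, agreement 75%

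A tetrachoric correlation estimates ρ. If usual care alone yields ρ of 0.4 to 0.6, the planned statistic would estimate that value in the DECIDES arms with no intervention effect. The argument does not depend on the particular figures; any non-zero alignment under usual care is enough.

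**4. What adding Usual Care could deliver.** Arm sizes are 10, 20 and 20 family units (6.2), so the pooled contrast is at most 10 versus 40. The share offered a trial is not given and is varied. With 80% aligned in both groups, the half-width of the 95% CI for the difference is 1.96 × √[0.8 × 0.2 × (1/n₁ + 1/n₂)]:

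- All offered, 10 versus 40: 1.96 × √(0.16 × 0.125) = 0.28
- Half offered, 5 versus 20: 1.96 × √(0.16 × 0.25) = 0.39
- 30% offered, 3 versus 12: 1.96 × √(0.16 × 0.4167) = 0.51

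Exact Fisher power (two-sided 0.05) for an assumed 50% versus 80% aligned is 13%, 23%, 30% and 44% when 30%, 50%, 70% and 100% are offered a trial. The contrast can be estimated but not usefully tested.

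**5. Which statistic by arm.** In simulation with a true value of 0.5 (median cut-points, cosine approximation, 0.5 added to each cell), the tetrachoric correlation in Usual Care alone had a central 95% range of −0.47 to 0.89 at n = 10, with an empty cell in 34% of samples. At n = 5 the range was −0.65 to 0.90, with an empty cell in 81%. Percent aligned is the more workable summary for so small an arm.

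**The case against.** Four points can fairly be made for the plan.

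*Usual Care may have no value scores.* Section 6.2 names no instrument, and the PRPQ is described in section 5.2 as 12 items rated 1 to 5, with no rule for what counts as endorsing a factor for or against enrollment. The value clarification exercise is another candidate, and it is described only within the DECIDES arms; were it the source, the restriction in 2.2 would follow from the data. This stands as an ambiguity. Table 1 favours the PRPQ but does not settle the matter, so a reader who infers that Usual Care certainly supplies the same data at no cost goes further than the documents allow.

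*There is no success rule.* A reader might infer that the plan would declare DECIDES effective on a figure such as 68% to 75% aligned. It does not plan to report percent aligned, and it states no threshold. The defect is that the planned result cannot bear on the objective it is listed under, not that a false declaration is built in.

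*Ten Usual Care families are too few, and this is a feasibility study.* Both are true. The primary aim is acceptability and feasibility, and Hyp 2a and 2b carry the comparisons with Usual Care. This limits the consequence and rules out recasting Hyp 2c as a directional hypothesis of greater alignment under DECIDES. It does not make a one-group correlation evidence of efficacy.

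*Restricting to those offered a trial is natural.* Alignment of an enrollment decision is defined only for them, so within an arm this is the target population. It becomes a possible selection problem when arms are compared, because the offer may come after randomization. That providers are told the value clarification results is part of the intervention and not a flaw.

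**Conclusion.** The point holds in a limited form. Hyp 2c is listed under preliminary efficacy but, as worded in 2.2 and analysed in 6.2, cannot show an effect of DECIDES, because alignment under usual care is not set against it. This follows from the text and needs no numerical assumption; the 68% to 75% illustration rests on assumed margins and correlations.

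That Usual Care scores can be computed is likely from Table 1, but depends on the PRPQ being the source of the value scores. If they exist, the comparison would be descriptive, with a half-width of about 28 points at best and 39 points if half are offered a trial (80% aligned assumed), and wider if fewer are offered one. The consequence is moderate: one secondary hypothesis in a feasibility trial, correctable before analysis.

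**What to change.** 1. Reconcile section 2.2, which restricts Hyp 2c to the DECIDES arms, with section 6.2, which does not.
2. Name the PRPQ, in line with Table 1, as the source of the value scores in all three arms. Define which items count as supporting or not supporting enrollment, what response counts as endorsement, and how the two scores classify a decision as aligned.
3. Add a variable recording whether a trial was offered, and when relative to randomization. Hyp 2c needs this even as it stands.
4. Report for each arm the number offered a trial and the percent of decisions aligned with 95% CI, then the DECIDES-minus-Usual-Care difference with its CI. Present this as a descriptive estimate, not a powered or directional test, and note that restriction to those offered a trial may condition on a post-randomization event.
5. State that the DECIDES-only tetrachoric correlation is descriptive and not evidence of efficacy.

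If the value scores come instead from the value clarification exercise, item 5 is the part of the between-arm remedy that remains, and Table 1 needs to be brought into line with 6.2.

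Cost: wording in 2.2 and 6.2, a scoring rule, one added variable on trial offers and one table. With the PRPQ as source, no new questionnaires, visits or patients are needed. The downside is an imprecise contrast and a more modest claim.
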